Client linkage to care	Prop. of clients that went to a clinic to access HIV services	Adoption process (users)	Client	No. of clients reporting visiting a clinic / No. of referred clients	>20% increase
Recent HIV testing	Prop. of clients who completed any HIV testing since referral	Adoption secondary (clients)	Provider	No. clients reporting testing for HIV since referral/ No. of referred clients	>20% increase

¹Retention: >1 PrEP clinic visit (guidelines recommend first-time PrEP users return to a clinic after one month)

861

Primary adoption outcome. Our primary outcome is reported PrEP initiation among all referred peer clients, as reported by peer providers (Objective 4). We had originally planned to measure this as a self-reported outcome among peer clients but had a challenge reaching peer clients that were referred in the pilot study; thus, have decided to link measurement of our primary outcome to peer providers delivering the intervention, as is typical in many studies assessing the impact of secondary distribution delivery models. To validate this, we will collect a DBS sample from a subset of willing peer clients that return in person at Month 3 (approximately 23/arm) to measure concentrations of tenofovir diphosphate (TFV-DP) and emtricitabine triphosphate (FTC-TP) using a validated liquid chromatography tandem mass spectrometry^{73,17}. Any concentrations of TFV-DP in a DBS sample will confirm PrEP initiation and/or adherence.¹⁶ In sensitivity analyses, we will measure our primary outcome using self-report data from peer clients (not providers) on PrEP initiation.

872

Secondary adoption outcomes. We will also measure secondary and process outcomes of peer clients as reported by peer providers, including number of peers referred, recent HIV testing, and PrEP continuation (e.g., peer clients that returned to the clinic and refilled PrEP drugs one month following initiation). As in the primary analysis, we will measure these outcomes using reported data from peer clients (not providers) in sensitivity analyses. We will also measure some secondary and process outcomes of peer clients as reported by themselves, including PrEP adherence (measured using a standard scale), HIVST use, and linkage to care. Finally, we will also measure a secondary outcome of PrEP continuation among peer providers, as reported by themselves.

880

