#### **4.1. Primary & secondary PrEP outcomes**

Our primary trial outcome will be PrEP initiation among referred peers, as reported by Index peers at the 3-month follow-up visit, **Table 3**. We will categorize clients as having initiated PrEP if they went to a healthcare facility (or other location) and were dispensed PrEP pills—consistent with how PrEP initiation is being measured in other PrEP implementation studies. We will also measure several secondary outcomes, including recent HIV testing, PrEP continuation, and PrEP adherence.

We are measuring all outcomes at 3 months to give referred peers time to both link to care, initiate PrEP services, and complete their first PrEP refill one month later if they are interested in continuing services. Additionally, this period is close enough to when the intervention was delivered that we anticipate little recall bias. Because we had challenges following up with referred peers in the pilot study leading up to this cRCT, we will be measuring all primary outcomes and most secondary outcomes reported by index peers, who are easier to follow-

up with and will report outcomes on behalf of the peers they recruited, as is typically done in interventions that utilize secondary distribution models. However, we will do our best to follow-up with referred peers and will measure our PrEP adherence outcomes reported from this population (we will also measure our primary and other secondary outcomes reported among this population and report them in sensitivity analyses).

Retention window (3 months): While most participants return for follow-up close to the scheduled 3-month visit date, operationally the scheduling window for this visit opens 2 weeks prior this scheduled visit date and closes 2 weeks after the scheduled date, unless a longer window was specifically requested by the participant. For our primary analysis, we will use follow-up visits assigned as 3-month visits by study staff.

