**Table 3. Detailed description of Peer PrEP cRCT primary and secondary outcomes**

Outcome	Definition	Reported by	Timing
PrEP initiation*	% of referred peers that went to a clinic and were dispensed PrEP pills , among those referred	Index peers*	Month 3
Recent HIV testing	% of referred peers who tested for HIV (any form of testing, including HIVST) since peer PrEP referral, among those referred.	Index peers	Month 3
PrEP continuation	% of referred peers that returned to a clinic to refill PrEP , among those referred. 	Index peers	Month 3
	% of index peers that returned to a clinic to refill PrEP , in the past 3 months (i.e., since peer referral)	Index peers	Month 3
PrEP adherence	Median of Wilson et al's 0-100 point adherence score,  with higher scores indicating higher adherence 	Referred peers	Month 3

\* Primary outcome

In prior versions of the SAP (v1.5), this was conditional among clients who initiated PrEP, but we changed to make it unconditional to align with the intent-to-treat analysis plan (described below) and best RCT practices on 07/11/2024—prior to study unblinding—per the recommendation of our DSMB.

Wilson, I. B., et al. (2009). "Improving the self-report of HIV antiretroviral medication adherence: is the glass half full or half empty?" *Curr HIV/AIDS Rep* 6(4): 177-186.

In prior versions of this SAP (v1.4), we had suggested an adherence threshold based on the Wilson et al score, but on 3/22/2024—prior to study unblinding—we decided to turn this into a continuous outcome after observing low continuation and thus low adherence in the past month among referred peers in review of the aggregate data across study arms in our DSMB.

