### ***10.2. Effect size estimation***

Our main analysis will evaluate the difference in proportion of PrEP initiation between referred peers in the enhanced and standard groups, as reported by index peers at Month 3. Secondarily, among referred peers at Month 3, we will evaluate the difference in proportions for recent HIV testing (since referral) and PrEP continuation (i.e., PrEP refilling) and median difference for self-reported PrEP adherence (using 100-point validated scale).

Our analysis is prespecified as intention to treat (ITT), using complete-case information and standard errors clustered at the level of the peer provider. We will estimate risk differences (RD) with 95% confidence intervals (CI) for binary outcomes using mixed-effect models with Gaussian distributions, identity links, study group fixed effects, and index peer random effects to adjust for clustering. For continuous outcomes, we will estimate median differences (MDs) using linear quantile mixed methods with the same specifications as those described above.

All the analyses will consider an alpha level of 0.05 as significant and will be run in R Studio (RStudio: Integrated Development Environment for R. Posit Software, MA 2025).

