### ***10.3. Missing values and “don’t know” responses***

Any missing observation due to data entry delays or CommCare skip logic conditions will be treated as failure. Similarly, any peer client’s outcomes reported by Index peers with “don’t know” responses, will be treated as failure.

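### Adherence score: the value for a woman who never started PrEP is implied but not stated, and the only planned comparison, a median difference, is 0 if more than half of reached peers in each arm score 0

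*SAP*

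**What the plan says.** SAP Table 3 defines PrEP adherence as the median of a "0-100 point adherence score", reported by referred peers at Month 3. Two footnotes to that row matter. Footnote 1 says of the previous definition that "this was conditional among clients who initiated PrEP, but we changed to make it unconditional". Footnote 3 explains why an adherence threshold was dropped: "we decided to turn this into a continuous outcome after observing low continuation and thus low adherence in the past month among referred peers". It says this was seen in data pooled across arms.

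For the analysis, SAP 10.2 says: "For continuous outcomes, we will estimate median differences (MDs) using linear quantile mixed methods with the same specifications as those described above". The same section describes the analysis as intention to treat, "using complete-case information and standard errors clustered at the level of the peer provider". SAP 10.3 adds that observations missing through data entry delays or "CommCare skip logic conditions will be treated as failure".

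No section gives the number that failure takes on a 0 to 100 scale. SAP 10.4 names no adherence analysis: its items that use index-peer reports cannot apply to a score reported by referred peers, and its referred-peer item would only repeat the main adherence analysis. Protocol Table 8 sets an increase of more than 20% in the median score as the metric for progression.

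**The concern.** Once non-starters are kept in, every one of them belongs at the bottom of the scale, together with starters who took no PrEP in the recall period. A median cannot see past a majority of equal values. With more than half of each arm at 0, it shows neither a difference in how many women use PrEP nor a difference in how well users take it. With one arm just below half and the other just above, it shows a large difference that mainly reflects which side of 50% each arm fell on. Footnote 3 replaced a threshold with a continuous score because adherence was low, and the median brings back a cut at 50% users.

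At stake is a named secondary outcome. It could be reported as a median difference of 0 when mean scores differ, or as a very large difference when they differ modestly. The progression metric has no relative reading if the control median is 0. The missing scoring rule adds to this, because an analyst who drops skipped cases would restore the conditional analysis that footnote 1 removed.

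**Working it through.** **Planning inputs.** SAP 5.1 assumes 40 index peers per group, 3 referred peers each, an ICC of 0.05, and 63% versus 80% initiation for 80% power. Check: design effect 1 + (3 − 1) × 0.05 = 1.10; effective n = 120 / 1.10 = 109.1 per group; two-sided 5% power = 0.7985, which agrees. The documents give no power figure for adherence.

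**Scoring rule.** Table 3 footnote 1 keeps non-starters in. If the form skips adherence items for them (the questionnaire is not in the documents), complete-case alone would drop them. SAP 10.3, read as the specific rule for skip-logic gaps, keeps them as failures. That reading is coherent and points to 0, but 0 is not written.

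**When the floor arises.** Share scoring above 0 = initiation × share of initiators still scoring above 0. A sample median is 0 once that product is below 0.5.
- Standard: 0.50 / 0.63 = 79.4%.
- Enhanced: 0.50 / 0.80 = 62.5%.
- Across SAP Table 6: standard 50/69.1 to 50/54.2 = 72.4% to 92.3%; enhanced 50/85 to 50/75 = 58.8% to 66.7%.

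**Timing.** The score covers the past month and is taken at Month 3. SAP 4.1 allows women to "complete their first PrEP refill one month later if they are interested in continuing services", and a Protocol Table 8 footnote notes that "guidelines recommend first-time PrEP users return to a clinic after one month". The relevant share is therefore nearer those still taking PrEP than those who ever started.

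**Simulation (assumptions, not document figures).** Non-users score 0; use is beta-binomial with ICC 0.05; 40 clusters per arm; users' scores are uniform on 0–100, 1–60, 40–100 or 80–100 (means 50, 30.5, 70, 90); 4000 trials per case; means compared by t-test on cluster means. Expected mean difference = difference in share of users × mean user score; for 25.2% versus 44%, 0.188 × 30.5 = 5.7 to 0.188 × 90 = 16.9. Ranges span the four distributions, except that power in the 25.2 v 44 row comes from three (1–60 omitted).

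| Users, standard v enhanced | Both medians 0 | Mean difference | Power for mean, 3 reached / 1 reached |
|---|---|---|---|
| 20% v 40% (illustrative) | 98% | 6–18 | 77–90% / 37–50% |
| 25.2% v 44% (63% and 80% initiation; 40% and 55% still using) | 88% | 6–17 | 68–83% / 31–43% |
| 30% v 48.4% | about 60% | 6–17 | 62–79% / 26–39% |
| 40% v 58.9% | about 3% | 6–17 | 60–80% / 27–40% |
| 63% v 80% (all initiators above 0) | never | 5–15 | – |

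The 30/48.4 and 40/58.9 pairs are initiation rates from Protocol Table 10, reused here as assumed rates of use. At 40% versus 58.9%, exactly one median is 0 in 95–96% of trials, and the median difference averages 10 to 79 points against a mean difference of 6 to 17. At 63% versus 80% with all initiators above 0, the median difference is 4 to 17 points and behaves reasonably.

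With 63% versus 80% initiation and 80 / 70 / 60 / 50% of initiators in each arm still scoring above 0, both medians are 0 in 0 / 7 / 62 / 98% of trials. At 50%, power for the mean is itself only 18–26%.

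**Does the planned model escape?** A random-intercept median model (asymmetric Laplace likelihood; the SAP names no package) gave an estimate within 1 point of 0 in 60 of 60 trials at 20% versus 40%. At 30% versus 48.4%, with a finer numerical fit, 84% of trials with both sample medians 0 did so. The floor carries over in practice but is not an algebraic certainty.

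**The case against.** A reader might infer that SAP 10.2 and 10.3 contradict each other on what a non-starter scores. They do not: neither states a score, and 10.3 reads naturally as the exception for skip-logic gaps. What stands is that failure has no stated value.

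A reader might also infer that the adherence result is bound to be 0. The documents do not support that either. They give no share of zeros, and at the planned initiation rates the floor is absent if initiators go on scoring above 0. The Protocol's data collection overview also places starting at about one month and the refill at about three months after baseline, which leaves less time for drop-off than the one-month refill interval suggests. Footnote 3 makes a majority of zeros realistic, not established.

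The strongest objection is that the median was specified consistently, and that a typical score of 0 in both arms is a correct answer to the question it asks. That is fair, and it is a reason to keep the median. It does not make the median sufficient as the only comparison.

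Finally, SAP 10.4 compares continuation as reported by the same reached referred peers, and unconditional continuation is a secondary outcome. These cover part of the any-use difference, but a refill is neither past-month use nor quality of use. The dried blood spot subset (about 23 per arm) has no stated arm comparison and may not be tested.

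**Conclusion.** The point holds in a limited form. The scoring rule is implied rather than written, and the single planned comparison can return 0, or a jump of tens of points, for reasons unrelated to the size of the difference in adherence. The floor statement is exact for sample medians and holds in practice, not by algebra, for the quantile mixed model. It rests on non-users scoring 0 and on more than half of reached peers in both arms doing so. At 63% versus 80% initiation, that means fewer than 79.4% and 62.5% of initiators still scoring above 0. The simulated percentages depend on assumed use rates and score distributions. The change is worth making because it is cheap, but it concerns one self-reported secondary outcome. The primary outcome is untouched.

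**What to change.** In SAP 10.3, state that a reached referred peer whose adherence items are skipped because she never started, or took no PrEP in the score's recall period, scores 0. Keep the reported score for anyone with use in that period, so that recent stoppers are not overwritten. Apply complete-case to peers not reached and to takers with unanswered items.

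In 10.2 and 10.4, keep the pre-specified median difference. Add the difference in the share scoring above 0 and the difference in mean score, by arm and clustered by index peer, both from the Gaussian mixed model already specified. Say that these carry the interpretation if either arm's median is 0. Read the Protocol Table 8 adherence metric on the mean scale if the control median is 0.

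The cost is a few sentences, two further runs of a planned model and a small edit to Protocol Table 8. The mean mixes any use with quality of use, so the share above 0 must be shown beside it. Power is modest if few peers are reached: 26–50% with one per index peer in the four tabulated cases where it is given, and lower where the arms differ little in use. If unblinding has occurred, the additions must be labelled post hoc.

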### ***10.3. Missing values and “don’t know” responses***

Any missing observation due to data entry delays or CommCare skip logic conditions will be treated as failure. Similarly, any peer client’s outcomes reported by Index peers with “don’t know” responses, will be treated as failure.

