 904 predictor: study arm; standard errors adjusted for clustering by peer provider). All analyses comparing
 905 randomization arms will be intention-to-treat, complete case analyses conducted at the unit of the
 906 individual (either peer provider or peer client). The primary comparison will be formalized peer PrEP
 907 referral + HIVST delivery versus informal peer PrEP referral (the standard of care). For analyses
 908 conducted at the level of the peer client, we will adjust standard errors for clustering at the peer provider
 909 level. We will use mixed-effect logistic regression models to measure risk ratios. All statistical test with 2-
 910 sided p-values <0.05 will be considered statistically significant. We will complete all analyses in R and
 911 STATA.

912 *Sample size*

913 If we assume that peer providers refer 75% of the targeted peer clients, this leaves us with three clients
 914 per peer provider, or 240 peer clients in total. We performed power calculations for our primary outcome,
 915 the proportion of referred peer clients who initiated PrEP at three months, in Stata 16.1 using methods
 916 for cluster-randomized trials, where each cluster is a peer group of one peer provider and three peer
 917 clients (**Figure 10**). **Table 10** shows the power we have to attain to detect various increases in the
 918 proportion of peer clients who initiated PrEP in the formal peer PrEP referral arm + HIVST (intervention
 919 group) vs. the informal peer PrEP referral arm (standard of care group). For our power calculations, we
 920 assumed 40 clusters (peer providers) per arm, 3 sampling units (peer clients) per cluster, and an intra-
 921 cluster correlation coefficient (ICC) of 0.05, which is standard for cluster-randomized controlled trials.
 922

925

Fig. 10. Power calculation to detect increase in the percentage (%) of referred peer clients initiating PrEP in the intervention group.

926

927

Table 10. Increase in the % of referred peer clients initiating PrEP in the intervention group. ICC: 0.05; clusters (providers) per arm: 40; units (clients) per cluster: 3 (75% of suggested clients referred)

Power (%)	Standard of care (%), p1	Intervention (%), p2	Increase (%), p2-p1
70	30	46.3	16.3
	40	56.8	16.8
	50	66.5	16.5
	60	75.7	15.7
	70	84.1	14.1
	80	91.7	11.7
80	30	48.4	18.4
	40	58.9	18.9
	50	68.5	18.5
	60	77.5	17.5
	70	85.7	15.7
	80	92.9	12.9
90	30	51.4	21.4
	40	61.7	21.7
	50	71.2	21.2
	60	79.9	19.9
	70	87.8	17.8
	80	94.5	14.5

928

929

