**Table 4. Detailed description of Peer PrEP cRCT process outcomes**

Process outcomes	Definition	Reported by	Timing
Peers referred	Number clients referred to PrEP services by index peers	Index peers	Month 3
HIVST use	% of referred peers in the enhanced group that used an HIVST (once; twice; or for partner testing)	Referred peers	Month 3
Client linkage to care	% of referred peers that went to a clinic to access HIV prevention/treatment services, among those referred	Referred peers	Month 3

Note: All outcomes binary.

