## **7. Data collection**

### **7.1. Database**

All quantitative data will be collected electronically in face-to-face and remote interviews with trained Kenyan research assistants. We will use CommCare (Dimagi, Cambridge, USA), an electronic data collection platform, to collect the quantitative data and will upload this data to CommCare's secure server daily. A team of data experts in both Partners in Health and Research Development (PHRD) and Seattle (Fred Hutch) will monitor the data as it is coming in, and Seattle team will generate weekly data quality reports that will be shared with the PHRD team for review and feedback.

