## **10.4 Sensitivity analyses**

- **Outcomes measured by referred peers (actual):** Measure effect estimate for peer client PrEP outcomes (e.g., initiation, recent HIV testing, continuation) as reported by referred peers, among those we were able to reach for follow-up.
- **Outcomes among all potential referred peers (n=320):** Measure effect estimates for referred peer PrEP outcomes (e.g., initiation, recent HIV testing, continuation) as reported by index peers, but among all potential referred peers index peers were recommended to recruit (n=320 clients, 4 per index peer)
- **Continuation among referred peers that initiated PrEP:** Measure effect estimates for peer client PrEP continuation as reported by index peers, among referred peers that initiated PrEP.
- **Treat “don’t know” responses as successes.** Measure effect estimates for referred peer PrEP outcomes (e.g., initiation, recent HIV testing, continuation) reported by index peers, but assume all “don’t know” responses are successes versus failures.
- **Multiple imputation of “don’t know” responses** via Markov Chain Monte Carlo under the assumption of missingness at random.
- **GEE approach:** Measure effect size estimates for referred peer PrEP outcomes (e.g., initiation, recent HIV testing, continuation) as reported by peer provider using the generalized estimating equations.

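### The protocol and the SAP name different primary effect measures with no note of the change, and SAP 10.3 scores observations missing through entry delay as failures in an analysis called complete-case (minor)

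*SAP*

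**What the plan says.** **Effect measure.** The protocol (Aim 2, Statistical analysis) names risk ratios, to be obtained from mixed-effect logistic regression. SAP 10.2 names risk differences with 95% confidence intervals, from a mixed model with Gaussian distribution, identity link and index-peer random effects. Both apply to PrEP initiation among referred peers. The footnotes to SAP Table 3 date two other changes (adherence on 3/22/2024, continuation on 07/11/2024) and place both before unblinding. No such note covers the effect measure.

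**Missing data.** The protocol says that comparisons between "randomization arms will be intention-to-treat, complete case analyses conducted at the unit of the" individual. SAP 10.2 likewise describes an intention-to-treat analysis "using complete-case information and standard errors clustered at the level of the peer provider". SAP 10.3 then says "Any missing observation due to data entry delays or CommCare skip logic conditions will be treated as failure", and it applies the same coding to don't-know answers given by index peers.

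**Sensitivity analyses.** SAP 10.4 lists six. Two vary the don't-know rule: one assumes that all such "responses are successes versus failures", and the other imputes them "via Markov Chain Monte Carlo under the assumption of missingness at random". The remaining four use referred peers' own reports, count all 320 potential peers, restrict continuation to initiators, and use GEE.

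**The concern.** A reader of the protocol expects a risk ratio as the primary result and a reader of the SAP expects a risk difference. The two are different estimates from different models. Without a record of when the choice was made, nobody can confirm from the documents that it preceded sight of results by arm. The protocol sentence also needs repair on its own terms, because a logistic model yields odds ratios and a risk ratio takes a further step.

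On missing data, scoring a blank as failure is single-value imputation, whereas complete-case analysis leaves the record out. For a record missing only because entry was late, the imputed value has no basis. If such blanks are unrelated to outcome and equally common in both arms, the risk difference shrinks towards zero. If they were more common in one arm, that arm would look worse even with no true effect.

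**Working it through.** **Inputs from SAP 5.1 and Table 6:** 63% (standard) and 80% (enhanced); 40 clusters of 3 per arm, so 120 referred peers per arm; ICC 0.05; power 80%. Alpha is 0.05 (SAP 10.2), two-sided (protocol, Aim 2, Statistical analysis). **Assumption:** a share r of individual records is blank, unrelated to outcome. The documents give no value for r.

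**Reproducing the plan's figure.** Design effect = 1 + (3 − 1) × 0.05 = 1.10. Effective n per arm = 120/1.10 = 109.1. In a two-proportion z-test with pooled null variance:

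- Null SE = √(2 × 0.715 × 0.285/109.1) = 0.0611
- Alternative SE = √((0.63 × 0.37 + 0.80 × 0.20)/109.1) = 0.0600
- z = (0.170 − 1.96 × 0.0611)/0.0600 = 0.836, so power is 79.9%, matching the stated 80%

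**Effect measures at the design rates.** RD = 0.80 − 0.63 = 0.170. RR = 0.80/0.63 = 1.27. OR = (0.80/0.20)/(0.63/0.37) = 2.35. The logistic model's natural output is on the third scale, not the second.

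**Blanks scored as failure, same r in both arms.** Each observed risk is multiplied by (1 − r), so RD = 0.170 × (1 − r). The risk ratio stays at 1.27 because the factor cancels. The rule therefore attenuates the SAP's chosen measure but not the protocol's.

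**Blanks left missing.** RD stays at 0.170, n per arm becomes 120(1 − r), and the mean cluster size becomes 3(1 − r). At r = 2%: n = 117.6, design effect 1.097, effective n 107.2. At r = 5%: n = 114, design effect 1.0925, effective n 104.3.

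| Assumed r | Observed risks, failure coding | RD, failure coding | Power, failure coding | Power, left missing |
|---|---|---|---|---|
| 0 | 0.630, 0.800 | 0.170 | 79.9% | 79.9% |
| 2% | 0.617, 0.784 | 0.167 | 77.0% | 79.2% |
| 5% | 0.599, 0.760 | 0.162 | 72.7% | 78.1% |

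**Unequal blanks, no true effect.** With an extra share d in one arm and common risk p, the spurious RD is d × p. For d = 0.02 this is 0.02 × 0.63 = 0.013 or 0.02 × 0.80 = 0.016. This shows the mechanism only.

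**Skip-logic blanks.** These figures do not apply to a blank that follows a no. A refill item skipped because the peer was reported as not initiating is a true failure under the unconditional continuation definition in SAP Table 3.

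**Scope.** The calculation covers blanks within an index-peer survey that was received. SAP Table 3 defines initiation as the share "of referred peers that went to a clinic and were" dispensed pills, among those referred. The number referred "to PrEP services by index peers" is itself an index-peer report (SAP Table 4). A wholly missing survey therefore usually removes the denominator as well, and is not counted here.

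**The case against.** The strongest reply has four parts.

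- **SAP 10.3 can be read as a list of exceptions to 10.2.** This is a fair reading, so the two sections do not firmly contradict each other. Neither section says so, however, and a clause is needed.
- **The skip-logic rule is natural and needed.** This stands. A reader might infer that failure coding of skip-logic blanks is an error. The documents do not support that: the questionnaire is not among them, and no branch is shown in which an item is skipped after anything other than a no. Only a safeguard in the wording is warranted.
- **Entry-delay loss should be small.** SAP 7.1 describes electronic capture, daily upload and a team that "will generate weekly data quality reports". A delay would also more plausibly hold back a whole form than one item. This largely stands for practical effect, although SAP 7.1 describes procedures and gives no rate. It also suggests that the rule has little reason to be there.
- **The analysis of referred peers' own reports is a check from another source.** It is a partial one: it does not depend on blanks in the index-peer survey, but it covers only peers who were reached and leaves the rule itself untested.

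On the effect measure, the reply is that the SAP is the later text (it cites 2024 changes and 2025 software), its model is acceptable, and the protocol simply lagged. That explains the mismatch but does not supply the missing record. Nor do the documents support the stronger inference that the measure was changed after unblinding; they say nothing either way.

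**Conclusion.** Wrong as written, and minor. The textual findings are firm: two effect measures for one primary outcome with no dated note, and a failure rule for entry delays that does not fit the complete-case label and that no sensitivity analysis varies.

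The size is not firm. Every missing rate above is an assumption, and the figures also assume blanks unrelated to outcome and equal by arm. On those terms the cost is about 2 points of power at 2% missing and about 5 points at 5%, relative to leaving the records missing. A reader might infer a materially underpowered or biased trial. The documents do not support that: they give no missing rate, nothing suggests that entry delay differs by arm, and the data procedures point to a small practical effect.

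**What to change.** 1. **Effect measure.** Make the SAP risk difference the single primary measure and bring the protocol sentence into line with it. Add a dated SAP note stating when the measure changed and whether that preceded unblinding. If a risk ratio is also reported, state that it is obtained by marginal standardisation.
2. **SAP 10.3, entry delays.** Remove them from the failure rule. Resolve such records before database lock and leave any that remain as missing.
3. **SAP 10.3, skip logic.** Score a blank as failure only when the parent answer is no. Let a blank under a don't-know parent follow the don't-know rule and its sensitivity analyses.
4. **SAP 10.2.** State that scoring don't-know answers as failure is an explicit exception to complete-case.

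Once entry delays are removed and the skip-logic rule is limited in this way, no extra sensitivity analysis is needed. The cost is one protocol sentence, one dated note and short edits to SAP 10.2 and 10.3, with no new data and no change to the sample size.
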